9.3 Stratification Factors

There will be no stratification in this study.

Analysis of primary endpoints

The toxicity and MTD will be evaluated by reporting the DLTs obtained at each dose level, and reporting toxicities noted in tabular form.

9.4 Analysis of Secondary Endpoints

1. Overall Response is the best response by RECIST 1.1 criteria recorded from the start of the treatment until response assessment by PET-CT at 3 months post treatment as below. Estimates of response rates, local control, PFS and OS will be determined at the MTD level, including the expansion cohort. Each of these will be presented along with a 95% two-sided confidence interval appropriate to the outcome measure. For example, the PFS and OS will have confidence intervals presented for the median times.

2. FADD/ BIRC2 Copy Number Variation will be evaluated as a secondary endpoint to estimate if recurrent HNSCC are enriched for these alterations associated with worse prognosis and associated with response to birinapant and IMRRT. A bioinformatics analysis algorithm has been established for determination of copy number variation and somatic mutation calling, by comparison and validation with DNA from matched blood (13). Archived tumor samples will be subjected to exome sequencing to estimate copy number variations, from all evaluable patients.

Results will be classified according to whether they have a FADD and/or BIRC2 copy gain (more than 2 copies) or not (13), and this classification will be compared between patients who respond or do not respond, in a descriptive fashion. A Fisher's exact test will be used to provide a p-value to help interpret the potential importance of any association, but in the context of a limited size evaluation. The association between results according to whether or not they have a copy gain will be presented for OS and PFS, by comparing Kaplan-Meier curves with a two-tailed log-rank test. In addition, as exploratory analyses, the association between FADD copy gain and BIRC2 copy gain will individually be evaluated for any association with response.

The feasibility of detecting effects of birinapant and re-irradiation on pilot pharmacodynamic markers in fresh frozen tumor biopsies, including micro-western for decrease in drug targets IAP1/2; increase in apoptosis/necroptosis markers Caspase 3 and MLKL will be evaluated. If IAP1/2, CASP3, and MLKL were each obtained pre-treatment and at day 4 on treatment, with 16 total patients at the MTD, there would be adequate patients so that the differences could each be tested using a paired t-test (or a Wilcoxon signed rank test if the differences are not normally distributed) with at least 80% power with an effect size equal to 1.0 times the standard deviation of the difference, with a 0.01 two-tailed significance test. In addition, although with less power depending on the fraction of patients who respond, comparisons could be made of the changes in these parameters between patients who respond or do not respond.

9.5 Analysis of exploratory objectives:

To determine if mutational load detected with whole exome- sequencing influences response, differences in patterns noted can be compared descriptively between responders and non-responders.

To determine if PD-L1, CD8 T-cell tumor infiltration, TNF α , and other immune related biomarkers are associated with response, changes in these parameters from baseline can be compared between responders and non-responders using a Wilcoxon rank sum test. Any tests performed will be done without adjustment for multiple comparisons but in the context of the number of tests performed.

To determine pharmacokinetic of birinapant, bioanalytical measurements will be conducted on an ultra HPLC-MSMS system using a validated assay by the Clinical Pharmacology Program (CPP) at the NCI. These data will be used to monitor birinapant plasma concentrations in order to assess any PK changes with radiation, as well as to correlate with pharmacodynamic endpoints, clinical response, and toxicity.

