2 BACKGROUND

2.1 Head and Neck Squamous Cell Carcinoma

Head and neck squamous cell carcinomas (HNSCC) affect ~52,000 new patients and cause ~11,000 deaths in the U.S. annually (1). HNSCC include a subset linked to human papillomavirus (HPV+) with better prognosis, and an HPV- subtype linked to tobacco use and worse prognosis in patients receiving standard treatment. The Cancer Genome Atlas recently uncovered amplifications of chromosome 11q13/22 in ~30% of HNSCC associated with an HPV- subtype and worse 5-year survival of <50% (2). The 11q13/22 loci harbor genes Fas Associated Death Domain (FADD) and Baculovirus Inhibitor of apoptosis Repeat Containing (BIRC2/cIAP1). A mutually exclusive subset harboring mutations of caspase 8 (CASP8) affects an additional 10% of HPV- cases (2, 3). Further, deletions in Tumor Necrosis Factor Associated Factor 3 and overexpression of BIRC3 (cIAP2) are detected in ~20% of HPV+ HNSCC (2). Together, these genes encode proteins that form critical components of the Tumor Necrosis Factor

Receptor/Death Domain Receptor signaling complex, which is deregulated and implicated in cell survival and therapeutic resistance in cancer (3, 4). Significantly, our pan-cancer comparison of TCGA data reveals that HNSCC are among the cancers with the highest frequency of genomic alterations in these cell death pathway genes, making them a potentially important target for therapy(5). Of clinical importance, since FADD/BIRC2 are associated with worse prognosis in patients with HPV- HNSCC receiving standard treatment(2), patients with recurrent HNSCC should be enriched for FADD/BIRC2 amplification or CASP8 mutations.

Binding of TNF α , or other death agonists to their receptors typically leads to cell death via FADD through the activation of caspase-8 and induction of apoptosis, or alternatively, by activation of RIP kinase 1 (RIPK1), MLKL, and induction of necroptosis(6, 7); **Figure 1**. However, the cellular Inhibitor of Apoptosis proteins cIAP1 and 2 encoded by BIRC2/3, are key antagonists of cell death signaling by TNF/FADD/CASP8 and cytotoxic therapies. Of therapeutic significance, IAP degradation and cell death signaling may be enhanced by Second Mitochondrial Activator of Caspases (SMAC) released during cell death, or SMAC peptidomimetics(4, 8).

[figure not shown]

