9.2 Sample Size/ Accrual Rate

This trial will initially consist of a 4 dose levels 3+3 escalation phase; with up to 6 patients per dose level, up to 24 patients may be required to determine the MTD. Then, at the MTD, an additional 10 patients will be treated in order to determine more precise estimates of safety and toxicity of patients as well as to address secondary objectives. If there are 16 patients at the MTD including the expansion cohort, then there would be approximately 80% power to detect an effect size of 2.0 for a given test comparing two groups or comparing pre-treatment values to on-treatment values with a 1.0 effect size, with a 0.01 two-tailed significance test. This would be sufficient to allow for up to 6 tests to be performed while holding the overall significance level to 0.05, taking into consideration enough patients to allow for a Bonferroni correction. In practice, given the exploratory nature of the marker and related analyses, the results may be presented without any such formal correction, but in the context of the number of such tests performed. As an illustration, if IAP1, CASP3, and MLKL were each obtained pre-treatment and at day 4 on treatment, with 16 total patients at the MTD, there would be adequate patients so that the

differences could each be tested with at least 80% power with an effect size equal to 1.0 times the standard deviation of the difference, with a 0.01 two-tailed significance test. In addition, although with less power depending on the fraction of patients who respond, comparisons could be made of the changes in these parameters between patients who respond or do not respond.

If all dose levels are evaluated and 10 additional patients are included at the MTD, we anticipate enrolling a minimum of 16 patients and a maximum of 34 patients. It is anticipated that 1-2 patients/month may be enrolled onto this trial.

Primary endpoints will be the DLTs and other toxicities, and the MTD for the regimen.

For DLT and MTD determination, escalation will proceed with the 3+3 dose escalation design until either the stopping rule below or the MTD is reached.

No. of patients with DLT's at this dose level	No. of patients treated at this dose level	Action
Dose escalation rules		
0	3	Treat 3 patients at the next higher dose level (or add 3 patients if at the highest level).
1	3	Treat 3 additional patients at this dose level.

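### Section 9.4 tests OS and PFS by copy gain with an ordinary log-rank test in 16 to 34 patients; at nominal 0.05 its true size is about 0.06 to 0.07, which an exact version would correct (minor)

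*Combined protocol and SAP*

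**What the plan says.** Section 9.4, item 2, classifies each patient as having a FADD and/or BIRC2 copy gain (more than 2 copies) or not. Two kinds of test then use that classification:

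- Response: "A Fisher's exact test will be used to provide a p-value", to be read with the limited size of the evaluation in mind.
- OS and PFS: the groups are compared "by comparing Kaplan-Meier curves with a two-tailed log-rank test". No exact or permutation version, minimum group size or minimum number of events is given.

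On numbers, Section 9.2 says "we anticipate enrolling a minimum of 16 patients and a maximum of 34 patients". Copy number is to be estimated "from all evaluable patients", not only from those treated at the MTD. The only frequency in the documents is in Section 2.1: "amplifications of chromosome 11q13/22 in ~30% of HNSCC". Sections 2.1 and 2.4 expect enrichment in recurrent disease but do not quantify it.

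Section 9.2 calls the marker analyses exploratory and allows results to be shown without formal multiplicity correction.

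**The concern.** The chi-square reference distribution for the log-rank statistic is a large-sample approximation. With few patients and unequal groups it is anti-conservative: under no association, p falls below 0.05 in more than 5% of trials. One paragraph therefore gives the same classification an exact p-value for response and, on the usual reading, an approximate one for OS and PFS.

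The association of copy gain with PFS and OS is a stated secondary objective (Section 1.2), and Section 2.5 says these markers may help judge their use for selection in later phase II studies. If p-values are shown without multiplicity correction, the reader relies on each one being calibrated.

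**Working it through.** **Plan's own figure.** The plan states no power, size or event count for the log-rank test. Its nearest figure is in Section 9.2, for a two-group comparison of a measured quantity: about 80% power at effect size 2.0, 16 patients, two-sided 0.01. Using the noncentral t with n1 + n2 − 2 degrees of freedom and noncentrality 2.0 × √(n1·n2/(n1+n2)):

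- 8 v 8: 2.0 × √(64/16) = 4.0, power 82.6%.
- 6 v 10: 2.0 × √(60/16) = 3.87, power 79.7%.

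That figure reproduces, but it says nothing about the calibration of the log-rank test.

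**Inputs for the size check.**

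- Total patients: 16 to 34 (Section 9.2).
- Gain frequency: about 30% (Section 2.1). 0.30 × 16 = 4.8, so 5 v 11; 0.30 × 22 = 6.6, so 7 v 15; 0.30 × 25 = 7.5, so 8 v 17; 0.30 × 34 = 10.2, so 10 v 24. Applying this figure to recurrent disease is an assumption, so other splits are shown.
- Event fraction: Section 2.4 cites 2-year OS of 15 to 38%, i.e. 62 to 85% dead by 2 years. PFS counts progression or death, so it has at least as many events over the same follow-up.

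**Statistic.** With one event at each time, U = Σ(d1 − n1/n) and V = Σ n1·n2/n², where d1 is 1 if the event is in the gain group and n1, n2 and n are the numbers at risk in the two groups and in total. The ordinary test rejects at 0.05 when |U|/√V > 1.960.

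**Size at 16 patients, all events observed, no ties.** Under no association every assignment of patients to groups is equally likely, so the size can be enumerated. For 5 v 11 there are 4,368 assignments, of which 314 reject: 314/4,368 = 0.0719.

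| Split | True size at nominal 0.05 | Ratio |
|---|---|---|
| 8 v 8 | 0.0668 | 1.34 |
| 6 v 10 | 0.0688 | 1.38 |
| 5 v 11 | 0.0719 | 1.44 |
| 4 v 12 | 0.0764 | 1.53 |
| 3 v 13 | 0.0857 | 1.71 |
| 2 v 14 | 0.1083 | 2.17 |

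Averaged over binomial splits of 16, the size is 0.077 at 30% frequency, 0.071 at 40% and 0.069 at 50%.

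**Larger samples, all events observed.** 22 patients: about 0.067 (7 v 15) and 0.064 (9 v 13). 25 patients: 0.066 (8 v 17). 34 patients: about 0.063 (10 v 24).

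**With censoring (simulated).**

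- 5 v 11: 1.41 times nominal with 85% events, 1.30 with 70%, 1.10 with 50%.
- 10 v 24: 0.059, or 1.18 times, with 85% events.

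Simulations that also covered several censoring patterns and PFS read on a scan grid gave about 6 to 8% for 4 or 5 gain patients among 16.

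**After the change.** A permutation log-rank test at 16 patients with all events observed has size 0.0499 to 0.0500 for every split from 2 v 14 to 8 v 8. With 1 v 15 it cannot reject at 0.05, since its smallest p-value is 1/16 = 0.0625.

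**The case against.** Several counter-arguments have force.

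- **Sixteen is probably too few.** It is the size of the MTD group ("If there are 16 patients at the MTD including the expansion cohort"), while the copy-number analysis takes all evaluable patients. The December 2022 cover letter indicates that neither of the first two dose cohorts had to be expanded, so about 3 + 3 had been treated. If level 2 became the MTD, a completed trial would have about 3 + 6 + 3 + 10 = 22 patients. Section 9.2 still prints 16 as the minimum, so 16 is the lower end and not the expected case.
- **The groups may be better balanced than 30 v 70.** The 30% is for amplification in unselected HNSCC. Section 9.4 counts any gain above 2 copies in either gene, and enrichment is expected. Balance reduces the inflation but does not remove it: 8 v 8 still gives 0.067.
- **The log-rank test is not labelled asymptotic.** An exact p-value would not contradict the text. The chi-square version is nonetheless the usual reading, and an exact test is named only for response.
- **Nothing is decided on these p-values.** This stands and limits the severity.

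A reader might infer more than the documents support, in three ways:

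- That the test rejects 1.7 times too often at 0.05, or three times too often at 0.01. Both figures need an assumed 3 v 13 split of 16. At 30% frequency a smaller group of 3 or fewer has probability about 0.25 with 16 patients and 0.07 with 22. Nor are they ceilings, since 2 v 14 is worse.
- That 0.01 is the threshold for these tests. Section 9.2 uses that level ("with a 0.01 two-tailed significance test") to plan effect sizes in standard-deviation units and sets no threshold for the log-rank comparisons.
- That Fisher's test was chosen because the sample is small. The plan gives no reason; its remark on limited size concerns interpretation.

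**Conclusion.** The point holds, at minor severity. Read in the usual way, the planned test is anti-conservative over the whole foreseen range of sample sizes: roughly 1.4 times nominal at 16 patients (5 v 11), 1.3 times at 22 to 25 and 1.2 to 1.25 times at 34. A printed 0.05 is then closer to 0.06 or 0.07.

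This rests on the chi-square version being used, a gain frequency near 30% or somewhat higher, most patients having an event, and few tied event times. Heavy censoring brings the size close to nominal; a very small gain group makes it worse. The evidence on a secondary objective would be modestly overstated, and no trial decision changes.

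**What to change.** In Section 9.4, item 2, for the OS and PFS comparisons by copy gain, replace 'two-tailed log-rank test' with 'two-tailed exact (permutation) log-rank test'. Report the number of patients and of events in each group beside each p-value.

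The cost is a few words and a few seconds of computing, with no added data or patients. P-values become slightly less favourable. The permutation test assumes similar censoring in the two groups, which are not randomised, so follow-up by group should be shown. If only one patient falls in a group, the result should be purely descriptive.

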1.2 Secondary Objectives

- Determine the objective response rate of patients with locoregionally recurrent head and neck squamous cell carcinoma (HNSCC) treated with re-irradiation and birinapant.
- Determine the local-regional control, progression free survival (PFS), and overall survival.
- Determine if FADD and/or BIRC2/3 copy gain in tumor tissue are associated with improved response, locoregional control (LCR), progression-free survival and overall survival.
- Determine the feasibility of detecting effects of birinapant and re-irradiation on pilot pharmacodynamic biomarkers in tumor tissue, by using microwestern to assess decrease in drug targets IAP1/2 and increase in apoptosis/necroptosis markers Caspase 3 and MLKL.

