3.1 Inclusion Criteria

- 3.1.1 Patients must have histologically or cytologically confirmed locally recurrent HNSCC, including nasopharyngeal or sinonal cancer for whom re-irradiation for local control is considered standard of care.
- 3.1.2 Patients with HPV-negative or HPV-positive head and neck cancer are eligible.
- 3.1.3 Patients who have had prior treatment with immune therapies are eligible.
- 3.1.4 Patients must have received curative-intent platinum- and/or cetuximab-based chemoradiotherapy or radiotherapy alone.
- 3.1.5 Patients must have completed their last treatment dose with chemotherapy or immunotherapy at least 4 weeks (6 weeks for nitrosoureas or mitomycin C) before enrolling on study.
- 3.1.6 Patients must have completed their last treatment dose with radiotherapy at least 6 months before enrolling on study.
- 3.1.7 Patients who have had major surgery must be fully recovered and require a recovery period of at least 4 weeks prior to enrolling on study.
- 3.1.8 Age ≥ 18 years.
- 3.1.9 ECOG performance status ≤ 2 (see [Appendix A](#)).
- 3.1.10 Patients must have normal organ and marrow function as defined below:

- Hemoglobin	≥ 9 g/dL (transfusion permitted)
- Absolute neutrophil count	$\geq 1,500/\text{mcL}$
- Platelets	$\geq 100,000/\text{mcL}$
- Total bilirubin institutional limits	within $1.5 \times$ the upper limit of normal (ULN)
- AST(SGOT)/ALT(SGPT)	$\leq 2.5 \times$ institutional upper limit of normal
- Serum creatinine	$\leq 1.5 \times$ upper limit of normal (ULN), OR :
Creatinine clearance	≥ 50 mL/min according to Cockcroft Gault formula or other institutional methods.
- Cardiac function	Patients must have a QTcF ≤ 480 msec.
- INR	INR ≤ 1.5 and no clinically significant bleeding event

within the past six months

- 3.1.11 Ability to understand and the willingness to sign a written informed consent document.
- 3.1.12 Patients must have measurable disease, per RECIST 1.1. See Section [12](#) for the evaluation of measurable disease.

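### Section 9.4 compares copy gain with no gain without regard to HPV status; showing the comparison by HPV status is a cheap improvement.

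*Combined protocol and SAP*

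**What the plan says.** Objective 1.2 is directional: "Determine if FADD and/or BIRC2/3 copy gain in tumor tissue are associated with improved response", and likewise locoregional control, PFS and OS.

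Section 9.4 sequences tumors from all evaluable patients and calls a tumor positive when FADD and/or BIRC2 exceeds two copies. For response, "A Fisher's exact test will be used to provide a p-value to help interpret the potential importance of any association", within a comparison described as descriptive and limited in size. OS and PFS are compared between gain and no gain "by comparing Kaplan-Meier curves with a two-tailed log-rank test". Neither test is adjusted.

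On the population, Section 3.1.2 states: "Patients with HPV-negative or HPV-positive head and neck cancer are eligible". Section 9.3 states: "There will be no stratification in this study". Section 9 does not mention HPV, and the Study Calendar lists no HPV item.

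On prognosis, Section 2.1 says "HNSCC include a subset linked to human papillomavirus (HPV+) with better prognosis" and reports "amplifications of chromosome 11q13/22 in ~30% of HNSCC associated with an HPV- subtype and worse 5-year survival of <50" percent. It also says that patients with recurrent disease should be enriched for these alterations, "since FADD/BIRC2 are associated with worse prognosis in patients with HPV- HNSCC receiving standard treatment".

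**The concern.** The protocol's own background links the marker to HPV status, and HPV status to prognosis. HPV-positive patients would then sit mostly in the no-gain group and lift its outcome. The pooled contrast mixes any effect of gain with the difference between HPV groups, and that mixing works against the hypothesis in objective 1.2. A real advantage of gain could be hidden, or an absent effect could look like harm.

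Copy gain is a named secondary objective and the first-priority integrated biomarker in Section 5.7, with mandatory specimens. Section 2.5 expects these markers to inform whether it is feasible to study them further as biomarkers in phase II. A caveat about small numbers does not warn the reader of a bias with a direction.

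**Working it through.** **The plan's own power figure.** Section 9.2 claims about 80% power with 16 patients at two-sided 0.01. Using the noncentral t distribution, a paired difference of 1.0 SD with n=16 gives 83.5%, and two groups of 8 differing by 2.0 SD give 82.6%. The figure reproduces, but it concerns continuous markers. No power is stated for the Fisher or log-rank copy-gain tests.

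**What the documents supply.** They give the direction only: HPV-positive is better, amplification is associated with HPV-negative, and most recurrences are HPV-negative (Section 2.4). They do not give the HPV-positive share *h*, the gain rates *g* (HPV-negative) and *g₊* (HPV-positive), or the HPV hazard ratio after re-irradiation. All of these are assumed below.

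**Step 1: make-up of the groups.** The HPV-positive share of the no-gain group is h(1−g₊) / [h(1−g₊) + (1−h)(1−g)].
- Strong inputs (h=0.30, g=0.50, g₊=0): 0.30/(0.30+0.35) = 46%, against 0% of the gain group.
- Mild inputs (h=0.20, g=0.50, g₊=0.20): 0.16/(0.16+0.40) = 29%, against 0.04/(0.04+0.40) = 9% of the gain group.

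**Step 2: response.** Assume response rates of 30% (HPV-negative, no gain), 50% (HPV-negative, gain) and 60% (HPV-positive, no gain). With the strong shares, the no-gain group responds at 0.462×60 + 0.538×30 = 43.8%. The true 20-point advantage within HPV-negative disease shows as 50 − 43.8 = 6.2 points. With g=0.30 the HPV-positive share is 38%, the no-gain rate is 41.4%, and the visible advantage is 8.6 points.

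**Step 3: pooled hazard ratio.** This is the large-sample Cox value for exponential survival, with HPV-negative no-gain median 12 months, a 24-month cut-off, g=0.40, g₊=0 and HPV hazard ratio 0.4.

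| True gain HR | h=10% | 20% | 30% | 40% |
|---|---|---|---|---|
| 1.0 | 1.14 | 1.28 | 1.43 | 1.57 |
| 0.7 | 0.80 | 0.90 | 1.00 | 1.10 |
| 0.5 | 0.57 | 0.65 | 0.72 | 0.79 |

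With g₊=0.20 and h=30%, a true 0.7 becomes 0.83 rather than 1.00. If HPV has no prognostic effect, 0.7 stays 0.70. If gain is equally common in both groups, it stays at 0.70-0.72.

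**Step 4: operating characteristics.** Simulated log-rank tests at two-sided 0.05, with HPV-negative no-gain median 9 months, censoring at 24 months and g=0.50. The pooled statistic is Σ(O−E)/√ΣV over all patients. The stratified one computes O−E and V within each HPV group and then sums. At n=34:

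| h, HPV HR, g₊ | Significant harm, no true effect: pooled / stratified | Power at gain HR 0.5: pooled / stratified |
|---|---|---|
| 30%, 0.4, 0% | 19% / 2.5% | 7% / 28% |
| 30%, 0.4, 20% | 9.5% / 2.0% | 16% / 31% |
| 20%, 0.6, 20% | 5% / 3% | 26% / 33% |
| 10%, 0.6, 0% | not tabulated | 30% / 36% |
| HPV not prognostic | no bias | 37% / 34% |

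The nominal rate for significant harm is 2.5%. At n=16, power is about 5-17% pooled and 18-22% stratified across the prognostic settings. Repeat runs move individual entries by one or two points, and put the n=16 stratified figures nearer 16-20%.

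**The case against.** Several points on the other side are sound.

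- **The pooled test is not invalid.** Objective 1.2 asks about association, and in an unselected population the pooled test validly tests the marginal association. A reader might infer an inflated type I error, but the excess of apparent harm is a real association that runs through HPV. The issue is which contrast answers the objective.
- **Amplification is associated with HPV-negative disease, not confined to it.** Section 9.4 counts anything above two copies, which is broader than amplification, so some HPV-positive tumors may be positive. The bias then shrinks, as shown above.
- **HPV-positive patients may be few.** Section 2.4 says most recurrences are HPV-negative, and no passage gives the HPV effect after re-irradiation.
- **n=34 is the ceiling.** The amendment letter reports that neither of the first two cohorts needed three more patients. With six at each of levels 3 and 4, the total is 3+3+6+6+10 = 28. At n=28 with weak inputs (h=20%, HPV HR 0.8, g₊=20%), power is 28.5% pooled against 29.8% stratified.
- **No decision rests on these p-values.** A reader might infer that they choose the phase II selection marker. Section 2.5 speaks only of the feasibility of further biomarker study, and Section 9.2 calls the marker analyses exploratory.
- **Section 9.3 is not a prohibition.** Its statement sits under stratification factors and need not exclude a stratified analysis.

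These points limit the size and the consequence. They do not remove the mechanism, and the descriptive label does not warn of its direction. The worry that stratifying wastes power in a small trial has little force: in the prognostic settings tabulated, stratified power is higher, and if HPV is not prognostic the loss is small.

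**Conclusion.** The point holds as a cheap improvement, not as an error that invalidates the analysis. If HPV remains prognostic at recurrence and gain is less common in HPV-positive tumors, the pooled comparison leans against the improved outcome in objective 1.2. With n=34 and gain in half of HPV-negative tumors, the lean runs from modest to large, as the mild and strong rows of the simulation table show. The documents do not say where in that range the trial lies. The bias is absent if HPV is not prognostic or if gain is equally common in both groups.

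A reader might infer that stratifying by HPV would isolate a predictive effect. It would not. Section 2.1 reports gain as prognostic within HPV-negative disease too, and the trial has no control arm. Power is low either way, so a non-significant result, pooled or stratified, is not evidence that gain lacks predictive value.

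**What to change.** - Add HPV status as a baseline data item, taken from the pathology report already uploaded under Section 4.3.3, with an unknown category where it is not reported.
- In Section 9.4, present the copy-gain comparison by HPV status. Use an HPV-stratified log-rank test for PFS and OS and an HPV-stratified exact test for response, or HPV-negative patients only if no HPV-positive tumor has gain. Give effect estimates with confidence intervals, and keep the pooled result alongside.
- State that stratifying does not separate predictive from prognostic effect, that power is low, and that a non-significant result is not evidence of no predictive value.

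The cost is analysis-plan wording and one data item, with no extra patients or procedures. The downsides are that HPV-positive patients add little or no information when none has gain, that power falls slightly if HPV is not prognostic (37% to 34% in the case run), and that HPV status may be missing for some older tumors.
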